For years, hemostatic therapy in massively bleeding and/or transfused patients has been guided with standard coagulation tests (SCTs) such as prothrombin time (PT), prothrombin index (PTI), activated partial thromboplastin time (aPTT), international normalized ratio (INR), fibrinogen, and platelet count. However SCTs limitations include the inability to assess clot strength, fibrinogen functionality; it does not measure the functionability of the red blood cells, and it does not assess the response of all these factors to an injury or surgery. Another potential disadvantage in these tests, includes the turnaround time; which generally is >30 minutes, ranging between 29 to 235 minutes. All these factors contribute to delay the clinical decision in this dynamic setting. [8-10]

Recently, point of care (POC) monitoring has emerged as a valuable alternative in hemostatic therapy algorithms for trauma, transplant, and cardiac surgeries. Thromboelastography (TEG) and thromboelastometry (ROTEM) are viscoelastic coagulation monitors that have shown to have the

Protocol #:2014H0447

Version: 1.0

potential to provide a more updated and comprehensive overview of the coagulation status. They provide a closer approach to *"in vivo* coagulation", by measuring the entire clot process starting from fibrin formation until clot retraction and degradation (fibrinolysis). [8]

Rotational thromboelastometry (ROTEM) is a POC testing device commonly used to provide a global assessment of the hemostatic status by measuring multiple aspects of blood coagulation, including, the generation of thrombin, factor deficiency, platelet function, fibrinogen, fibrinolysis and the effect of heparin in the coagulation cascade. ROTEM provides the development of the clot via initiation, increased clot firmness and changes of blood clotting under low shear conditions. ROTEM can also monitor the *extrinsic coagulation pathway* in the **EXTEM** assay and the *intrinsic coagulation pathway* in the **INTEM** assay by adding ellagic acid. [11]

Different modifications can be made to both the EXTEM and INTEM in order to assess other various defects of hemostasis:

- 1. Addition of Cytochalasin-D in the *EXTEM* directly measures the fibrin contribution to the clot and indirectly assesses fibrinogen availability; called **FIBTEM test.**
- 2. When compared to the *EXTEM* assay, the addition of Plasmin inhibitor confirms fibrinolysis and demonstrate efficacy of antifibrinolytic therapy: **APTEM test**.

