The power analysis has been calculated based on a mean estimated RBC transfusion of 8 units with a conservatively estimated standard deviation of 5. We expect that ROTEM will decrease the RBC transfusion by 3 units. We make the same assumptions for FFP. We will test each main outcome between the ROTEM and control groups at an alpha of 0.025 (adjusted for 2 main outcomes). We need 110 patients; 55 patients in each group to achieve 80% power to detect a difference of 3 units assuming a standard deviation of 5 at an alpha of 0.025.[3,13]

4. Randomization and study procedures:

Patients will be randomized in a 1:1 ratio to either laboratory coagulation tests or ROTEM. No changes in surgery or anesthesia technique will be made for study's purposes.

a. Laboratory Coagulation Tests

If the patient is randomized to laboratory coagulation tests, anesthesia care providers will assess the hemostatic status according to OSUWMC standard practices and their own clinical criteria.

Laboratory coagulation tests include but are not limited to the following: hemoglobin, platelet count, fibrinogen concentration, INR, aPTT, and PT. These assessments will be performed at fixed perioperative time points (preoperatively, every 2 hours intraoperatively, end of surgery (EOS), and 24 hours after EOS). Intraoperative arterial blood gases will be performed repetitively

Protocol #:2014H0447 Version: 1.0 at a fixed range (every hour) based on anesthesia care provider's decision, along with any other common laboratory tests.

b. ROTEM

If the patient is randomized to ROTEM, the anesthesia care provider will be blinded to any conventional intraoperative coagulation test that might be performed during surgery.

ROTEM will be used according to the manufacturer's instructions using equipment and test reagents provided by Tem International GmbH. All tests will be performed at the bedside by a healthcare provider trained to perform ROTEM. A specific algorithm has been created by [name] (Clinical Director at Tem International GmbH-ROTEM) and should be followed according to measurements obtained during surgery (Figure 1).

ROTEM monitoring will be performed in patients with signs of clinically relevant diffuse bleeding and in whom blood transfusion is considered (Temp >35°C; pH <7.2; Cai >4.6 mg/dL; Hb \ge 9g/dL, or >10g/dL with anticipated greater blood loss) or at a fixed range every 2 hours or at Anesthesiologist criteria based on patient's clinical situation.

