Patient's clinical situation should be consider as the most important component on the transfusion decision-making process. Packed erythrocytes will be transfused to maintain hemoglobin concentrations >9g/dl or >10g/dl in individuals with underlying cardiovascular disease or anticipated greater blood loss. Individual based dynamics (tachycardia, hypotension, sings of ischemia on electrocardiogram, and lactic acidosis) strongly indicating the need for erythrocyte transfusion will be also part of the decision-making transfusion process by the anesthesia care provider.

5. Data collection

The following data points will be recorded in the interventional and control group patients:

- Demographic information (age, sex, height, weight, BMI, race)
- Medical History (including past and current diagnosis, use of chemotherapy or radiation, type of cancer, medications, surgical history)
- Surgical Information (Procedure type/reason for surgery, length of surgery, perioperative medications, ASA physical classification, type of anesthesia)
- Anesthesia record information
- Baseline (pre-operative) and perioperative coagulation lab values (PT, PTT, INR, HTC, HTC, PLT, FIB) (followed for 24 hours postoperatively)
- Perioperative ROTEM values
- Baseline and perioperative hemodynamics (BP, HR, RR, OXYGEN SATURATION, Temperature).
- Intraoperative arterial blood gases
- Intraoperative blood loss (over time)

Protocol #:2014H0447

Version: 1.0

- Transfusion information (type of product, number of transfused units, time administered) intraoperative and 6, 12, and 24 postoperative.
- Use of other hemostatic therapy
- Use of antifibrinolytic agents
- Intraoperative fluid management (type, volume, and frequency)
- Urine output for the first 24 hours.
- Postoperative time of mechanical ventilation
- Length of ICU stay and hospital stay
- Other intraoperative and postoperative complications (including respiratory failure, overall infection rate)
- Inpatient mortality
- Postoperative Day 30 phone call follow-up to assess serious adverse events and mortality.
- Hemostatic therapy cost assessment

IV. Assessment and reporting of Adverse Events and Serious Adverse Events

The occurrence of adverse events (AE) and serious adverse events (SAE) will be recorded from the time of consent until discharge. For each AE, the relationship to the study procedures and monitoring, severity, expectedness, outcome will be determined by the PI and recorded in the study source accordingly

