If the case a subject withdraws from the study due to a serious adverse event the local IRB will be notified within 10 days.

Adverse Event definition

An AE is defined as any untoward medical occurrence in a patient or clinical investigational subject who has undergone an investigational procedure and that does not necessarily have to have a causal relationship with the study treatment. An AE can be any unfavorable or unintended sign, symptom, abnormal laboratory finding, or a temporal disease associated with the study procedure and monitoring, whether or not considered related to the procedure. Planned hospital admissions and/or surgical operations for an illness or disease that existed prior the subject was enrolled in a clinical study are considered part of the subject's medical history and are not considered AEs.

Serious Adverse Event

A SAE is any untoward medical occurrence that at any dose:

- Results in death
- Is life-threatening
- Results in persistent or significant disability/incapacity
- Requires in-subject hospitalization or prolongs hospitalization

Version: 1.0

- A congenital anomaly/birth defect

- Is another medically-significant event that, based upon appropriate medical judgment, may jeopardize the subject and require medical or surgical intervention to prevent one of the outcomes listed above.

V. Withdrawal criteria from the study

Reasons for premature discontinuation

According with the Declaration of Helsinki, participants have the right to withdraw from the study at any time for any reason. The Principal Investigator also has the right to remove a subject from the study. Reasons that a subject may be removed from the study include:

- An AE or SAE

- The request of the subject, his/her legal representative or caregiver, or investigator, for administrative or other reasons

- Non -compliance with medication, protocol violation, or unreliable behavior

- Any clinically significant abnormalities identified by the Principal Investigator according to his clinical judgment will be followed by appropriate tests and/or procedures until these abnormalities have subsided, returned to to clinically-acceptable levels, or can be attributed to causes other than the study procedure.

The principal Investigator may withdraw an enrolled and treated subject from the study for any of the following reasons:

- Occurrence of a serious or intolerable adverse event
- Emergence of a clinically-significant change in laboratory parameters.

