- The subject requests to be discontinued from the study

- A protocol violation sufficiently serious as to require subject withdrawal

[figure not shown]
- General or specific changes in the subject's condition that render further treatment unreasonable or unsafe within the standards of clinical practice in the judgment of the Principal Investigator or treating physician.

Any subject may leave the study at any time. If a subject decides to stop participating in the study, there will be no penalty. The subject will not lose any benefits to which they are otherwise entitled. Their decision will not affect their future relationship with The Ohio State University.

Protocol #:2014H0447

Version: 1.0

VI.Figure 1. ROTEM Spine Surgery Algorithm

- ¹ Basic conditions:
 - Temp. >35°C; pH >7.2; Cai++ >4.6 mg/dL.
 - $Hb \ge 9 g/dL$.
- ² Antifibrionolytic therapy:
 - Dirkmann et al. Anesth Analg. 2014 (under review)
 - CT_{FIB} > 600 s represents a flat-line in FIBTEM
 - Chapman et al. J Trauma Acute Care Surg. 2013
- ³ Fibrinogen dose calculation:

- A10_{FIB} 9-12 mm: 50 mg/kg fibrinogen
 (2.5 mL/kg fibrinogen conc. or 5 mL/kg cryoprecipitate)
- A10_{FIB} ≤ 8 mm: 75 mg/kg fibrinogen
 (3.75 mL/kg fibrinogen conc. or 7.5 mL/kg cryoprecipitate)
- ⁴ Platelet concentrate (PC) transfusion:
 - A10_{EX} 35-44 mm: 1 pooled or apheresis PC
 - \circ A10_{EX} < 35 mm: 2 pooled or apheresis PC
 - A10_{EX} \leq 25 mm: Platelet conc. + fibrinogen
- ⁵ If Prothrombin-Complex-Concentrate (PCC) is not available:
 - o 10-15 mL/kg FFP or
 - \circ 45-90 µg/kg rFVIIa (if A10_{EX} and A10_{FIB} are ok but FFP is not effective)
- Simultaneous interventions:
 - Maximum three interventions at the same time (In first analysis and severe bleeding)
 - Maximum two interventions at the same time (In second analysis and moderate to severe bleeding)
 - Only one intervention
 (In second or later analysis and mild to moderate bleeding)

Version: 1.0

Protocol #:2014H0447

Version: 1.0

VIII. REFERENCES

- 1. Bilsky, M.H. and J.F. Fraser, *Complication avoidance in vertebral column spine tumors*. Neurosurg Clin N Am, 2006. **17**(3): p. 317-29, vii.
- 2. Elgafy, H., et al., *Blood loss in major spine surgery: are there effective measures to decrease massive hemorrhage in major spine fusion surgery?* Spine (Phila Pa 1976), 2010. **35**(9 Suppl): p. S47-56.

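### The ROTEM-arm blind has no stated release, short of withdrawal, for a critical conventional coagulation result or for a period without valid ROTEM

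*Combined protocol and SAP*

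**What the plan says.** Section III.4.b states that if a patient is randomized to ROTEM, "the anesthesia care provider will be blinded to any conventional intraoperative coagulation test that might be performed during surgery". The sentence has no exception. It does not schedule conventional tests in this arm; it covers those that happen to be done.

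Other provisions bear on the point:

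- **Repeat ROTEM (III.4.b).** Testing is triggered by relevant bleeding, "or at a fixed range every 2 hours or at Anesthesiologist criteria based on" the patient's condition.
- **Clinical judgment (end of III.4).** The patient's "clinical situation should be consider as the most important component on the transfusion decision-making process". The same paragraph sets hemoglobin targets and lists lactic acidosis among the signs that favor erythrocytes.
- **Abnormal findings (V).** "Any clinically significant abnormalities identified by the Principal Investigator according to his clinical judgment will be followed by appropriate tests and/or procedures". This sits in the list of reasons for removing a subject.
- **Withdrawal (V).** The Principal Investigator may withdraw a patient for "Emergence of a clinically-significant change in laboratory parameters", or for changes in condition that "render further treatment unreasonable or unsafe within the standards of clinical practice in the judgment of the Principal Investigator or treating physician".
- **Data (III.5).** The list includes the anesthesia record, transfusion times, ROTEM values and "perioperative coagulation lab values (PT, PTT, INR, HTC, HTC, PLT, FIB" values. It has no item for release of a masked result.

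**The concern.** Followed as written, the rule withholds information from the person choosing treatment, in one arm only. Two situations matter. In the first, a conventional test has been done, its result is critical, and the provider may not see it. In the second, the ROTEM device or reagents are unavailable or the trace is invalid. The provider then has no ROTEM result and is also barred from the laboratory substitute. These patients are enrolled because intraoperative blood products are expected, and Section III.3 assumes a mean of 8 RBC units, so a period without coagulation data could be clinically important.

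There is a smaller consequence for the trial's answer. Clinicians facing either situation may break the blind anyway. The anesthesia record, laboratory values and transfusion times might allow some of these releases to be reconstructed, but nothing in III.5 asks for the time or the reason.

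**Working it through.** **Step 1: what is masked.** Sections III.1 and III.4.a between them list hemoglobin, platelets, fibrinogen, INR, PT, aPTT and ABG as laboratory coagulation tests. ROTEM-arm care must act on hemoglobin, pH and ionized calcium (III.4.b and the Figure 1 notes) and on lactic acidosis (end of III.4). Hemoglobin and blood gases must therefore stay visible. That leaves PT/INR, aPTT, platelet count and laboratory fibrinogen.

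**Step 2: does any provision release a masked result?**

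| Provision | What it allows | Releases a result to the blinded provider? |
|---|---|---|
| ROTEM on demand (III.4.b) | A further ROTEM | No, and no help if ROTEM is down |
| Priority of the clinical situation (end of III.4) | Weighing what the provider can see | Not stated; masked results are not mentioned |
| Follow-up of abnormalities (V) | Tests or procedures once the Principal Investigator identifies a problem | Not stated; no threshold and no duty to tell the provider |
| Withdrawal (V) | Leaving the study | Possibly, but participation ends |
| PCC unavailable (Figure 1, note 5) | FFP or rFVIIa | No; covers a product, not the device |

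None is an explicit release short of withdrawal.

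**Step 3: size of the exposure.** The rule covers all 55 ROTEM patients, but that is its scope and not a count of patients at risk. No conventional intraoperative test is scheduled in this arm and no ROTEM failure rate is given, so the number affected cannot be estimated and may be zero. While ROTEM works, a repeat may also be more current than the laboratory: the background text gives a laboratory turnaround "which generally is >30 minutes, ranging between 29 to 235 minutes".

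**Step 4: what a release would cost in power.** Inputs from III.3: 55 per arm, difference 3 units, SD 5, alpha 0.025 per outcome. Sidedness is not stated; a two-sided two-sample t-test is assumed.

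- Plan's own figure: d = 3/5 = 0.6. The noncentral t calculation requires n = 54.08 per arm, so 55 per arm and 110 in total, as stated. At 55 per arm the noncentrality is 0.6 × √(55/2) = 3.146 on 108 df, and power is 80.7%.
- Suppose k ROTEM patients have a release and each loses L units of benefit. The arm difference becomes 3 − L × k/55, with the SD held at 5. Both k and L are assumptions; the documents give neither.

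| k | L = 1.5: difference, power | L = 3 (whole assumed benefit): difference, power |
|---|---|---|
| 0 | 3.000, 80.7% | 3.000, 80.7% |
| 1 | 2.973, 80.0% | 2.945, 79.2% |
| 5 | 2.864, 76.6% | 2.727, 72.1% |
| 10 | 2.727, 72.1% | 2.455, 61.9% |

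Allowing the ROTEM-arm SD to rise because released and unreleased patients are mixed, √(25 + 9f(1−f)) with f = k/55, changes the L = 3 column only slightly: 79.0%, 71.4% and 60.6% for k = 1, 5 and 10.

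These figures price critical-value releases. They do not measure harm from the present rule. When ROTEM has failed, its benefit may be lost whether or not a laboratory result is released, so little of that loss belongs to the fix.

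**The case against.** The best case for leaving the text alone has four parts.

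- **The blind cannot be absolute.** The ROTEM-arm rules depend on hemoglobin, pH and calcium. A reader might infer from the word any that these too are hidden; the protocol's own treatment rules contradict that. For the tests that are masked, EXTEM, INTEM and FIBTEM and the A10-based dosing give related information. This stands, and it narrows the point, but it does not help when ROTEM is not working.
- **There is a partial route short of withdrawal.** Only the anesthesia care provider is blinded. The Principal Investigator could identify an abnormality and have it followed up, and the clinical situation ranks first in transfusion decisions. This lowers the practical risk. It is still not a release rule: the visible text names nobody to watch masked results during surgery and requires nobody to inform the provider.
- **A fallback may exist out of sight.** The Figure 1 flowchart is not visible, and its notes already contain one availability contingency. Hospital critical-value practice may also apply. Neither can be ruled out. If either covers the gap, a citation in III.4.b is all that is needed.
- **The harm is unquantified and the power figures are hypothetical.** Both are true. A reader might infer that critical results will be withheld from ROTEM patients, or that the power losses show damage already built into the trial. The documents support neither: masked tests are unscheduled, and k and L are assumed.

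**Conclusion.** The point holds in a limited form, as a cheap improvement that should be made. Section III.4.b states an unconditional blind, and no visible provision short of withdrawal lets the provider see a critical conventional coagulation result or obtain one while ROTEM is unavailable or invalid. This is more than missing detail, because a stated rule followed as written would withhold the information.

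The added risk is small while ROTEM works. The number of patients affected is unknown and may be zero. A reader might go further and infer that the protocol puts its own algorithm ahead of the patient, or makes the ROTEM arm unsafe. The documents do not support that, since they rank the clinical situation first and allow withdrawal on safety grounds.

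The conclusion assumes that hemoglobin and blood gases remain visible and that the unseen flowchart holds no fallback. Confidence is medium for that second reason.

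**What to change.** Add one sentence to Section III.4.b: the blind does not block (a) notification of a conventional result that meets critical-value limits set before enrolment, for which the hospital's existing limits may be cited, or (b) conventional results requested while ROTEM is unavailable or its result is invalid; and it does not override the priority that Section III.4 gives to the patient's clinical situation.

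Add one case-report-form line for the time and reason of each release. Keep the patient in the assigned arm for analysis, and report the number of releases in the ROTEM arm.

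The cost is that sentence, a short list or citation of limits, and the form line. The downside is some dilution of the contrast from releases under (a), growing with their number as shown in the working; this is a reason to set the limits narrowly. Under (b) the fix itself adds little to the loss.

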- Compare the amount of Cryoprecipitate and Platelets transfused intraoperative between both groups.
- Compare the amount of all blood products transfused at 6, 12, and 24 hours postoperative.
- Compare the incidence and requirements of fibrinogen concentrate, PCC, antithrombin concentrate, factor XIII concentrate, and activated recombinant factor VII, or any other hemostatic therapy. Compare variables that affect coagulopathy such as acidosis and hypothermia.
- Compare hemodynamic variables (BP, HR, O2, Temperature, Arterial blood gases) during surgery.
- Compare postoperative time of mechanical ventilation
- Compare length of ICU stay and overall hospital stay
- Compare total in hospital need for transfusion
- Compare postoperative coagulation status on days 1 and 3 if available
- Compare overall infection rate
- Compare 30 days mortality

3. Exploratory objectives

Compare the total costs of intra-operative blood transfusion guided with ROTEM versus laboratory coagulation tests in patients undergoing major spinal surgeries.

III. Material and methods

1. Study design:

This is a prospective, randomized parallel-group, single center study in patients undergoing elective major spine surgery. Patients will be randomized to guide blood transfusion administration with ROTEM or laboratory coagulation tests (ABG, PT, PTT, aPTT, Hb, platelets,

Version: 1.0

and fibrinogen). Randomization list will be computer-generated using a balanced allocation ratio 1:1.

- 2. Inclusion and exclusion criteria:
- Inclusion criteria
- 1. Male or female age 18 years or older.
- 2. Able to provide inform consent.
- 3. Patients schedule to undergo elective major spinal, orthopedic, or combined procedures under general anesthesia that are expected to receive intraoperative blood products and last greater than 2 hours.
- Exclusion criteria
 - 1. Subjects younger than 18 years old.
 - 2. Subjects who are prisoners.
 - 3. Subjects who refuse transfusion of blood products.
 - 4. Subjects unable to participate in the study for any reason in the opinion of the Principal Investigator.
 - 5. Subject with past medical history of uncontrolled coagulopathies.

3. Study population and sample size:

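### The only written haemoglobin target for red cells sits under the ROTEM arm, so the RBC rule can differ by arm on a main outcome

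*Combined protocol and SAP*

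**What the plan says.** Section III.4 has two lettered parts, one per arm.

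- **III.4.a (control).** The instruction is that "anesthesia care providers will assess the hemostatic status according to OSUWMC standard practices and their own clinical criteria". A schedule of laboratory tests follows. No haemoglobin trigger or target for red cells is given.
- **III.4.b (ROTEM).** The last paragraph, just before Section III.5, sets the red-cell target: "Packed erythrocytes will be transfused to maintain hemoglobin concentrations >9g/dl or >10g/dl in individuals with underlying cardiovascular disease or anticipated greater blood loss". It opens by making the patient's clinical situation the leading consideration. It closes with an override: haemodynamic and ischaemic signs "strongly indicating the need for erythrocyte transfusion will be also part of the decision-making transfusion process by the anesthesia care provider".

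Two other places mention a haemoglobin level, and both are ROTEM text. One is the III.4.b condition for running ROTEM, which includes "or >10g/dL with anticipated greater blood loss". The other is footnote 1 of Figure 1, where Hb of at least 9 g/dL is a basic condition of the algorithm.

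Section III.4 opens with a statement for all patients: "No changes in surgery or anesthesia technique will be made for study's purposes". It contains no transfusion rule. Section III.3 makes RBC and FFP the two main outcomes: "We will test each main outcome between the ROTEM and control groups at an alpha of 0.025 (adjusted for 2 main outcomes".

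**The concern.** The stated contrast is in how coagulation is assessed. Red cells, as the III.4.b paragraph describes them, are given on haemoglobin and clinical signs, not on a ROTEM reading. The footnotes to Figure 1 give doses for fibrinogen, platelets and plasma or factor products, but none for red cells. So the ROTEM readings do not themselves require a different red-cell rule in the two arms.

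A provider treating a control patient would turn to III.4.a and find only local practice and personal judgment. A provider treating a ROTEM patient would find a target of >9 or >10 g/dL. Both know the arm, since one of them is running the bedside test and algorithm, and no masking of red-cell decisions is described.

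If the two rules differ in practice, the RBC comparison estimates ROTEM plus a change of threshold. A written target more liberal than local practice would hide a ROTEM benefit; a more restrictive one would create or enlarge it. Arm and rule would coincide, so the analysis could not fully adjust for the difference.

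**Working it through.** **1. Which arm does the paragraph cover?**

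- *For ROTEM only:* it lies under III.4.b with no heading in between; its higher threshold shares a condition with the ROTEM monitoring sentence ("or >10g/dL with anticipated greater blood loss"); and no sentence extends it to control.
- *For both arms:* it names no arm; it lacks the opening clause on random assignment that starts both III.4.a and III.4.b; and it adds cardiovascular disease, which the monitoring sentence does not mention.

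The text supports either reading, and nothing in the documents settles it.

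**2. Reproduce the plan's sample size.** Inputs from Section III.3: control mean 8 units, SD 5, difference 3 units, alpha 0.025 per outcome, 80% power, 55 per arm. The plan names neither test nor sidedness. A two-sided two-sample t-test is assumed because it reproduces the figure: the solution is 54.08, rounded up to 55 per arm (110 in total), with power 80.7%. A one-sided 0.025 test needs only 44 per arm (normal approximation) and does not match.

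**3. What a rule-driven gap would do (illustration only).** The documents give no local threshold, so the gap in RBC units is assumed at 0, 0.5 or 1 in either direction. One unit is 1/8 of the planned control mean and 1/3 of the planned effect.

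- SE of the difference = 5 × √(2/55) = 0.953
- df = 108; critical t = 2.273
- Net difference = true ROTEM saving ± gap
- Noncentrality = net difference / 0.953; for example, 1/0.953 = 1.05, 2/0.953 = 2.10, 3/0.953 = 3.15

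| Assumed gap (units) | 0 | 0.5 | 1 |
|---|---|---|---|
| No ROTEM effect: two-sided rejection | 2.5% | 4.5% | 11.5% |
| No ROTEM effect, gap favours ROTEM: false claim of benefit | 1.25% | 4.2% | 11.4% |
| True saving 3, opposing gap (net 3 / 2.5 / 2): power | 81% | 64% | 43% |
| True saving 3, gap in same direction (net 3 / 3.5 / 4): power | 81% | 92% | 97% |
| Coverage of the 97.5% interval for the ROTEM effect | 97.5% | 95.5% | 88.5% |

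The estimate moves by the whole gap: at 1 unit, a true saving of 3 averages 2 or 4. A normal approximation gives nearly the same figures (for a 1-unit gap: 11.7%, 44% and 97.5% for the first, third and fourth rows).

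**4. Can the target be applied in the ROTEM arm?** Section III.1 counts haemoglobin and blood gases among the laboratory coagulation tests ("Patients will be randomized to guide blood transfusion administration with ROTEM or laboratory coagulation tests (ABG, PT, PTT, aPTT, Hb, platelets"), and III.4.a also lists haemoglobin. III.4.b blinds the provider to conventional intra-operative coagulation tests. Taken literally, that would hide the value the red-cell target depends on. The ROTEM conditions themselves use Hb and pH, so this is presumably not intended, but it is not stated.

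**The case against.** The strongest reply is that this is a matter of placement. The protocol does not use its headings strictly: the laboratory and blood-gas schedules appear only under III.4.a, yet Section III.5 introduces its list, which includes those tests, with "The following data points will be recorded in the interventional and control group patients". That phrase might suggest that the protocol always names both groups when it means both. It does not: the adverse-event and withdrawal sections cover everyone without saying so. This stands, and the missing arm label is not evidence that the paragraph is ROTEM-only.

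Provider judgment leads in both arms, so the contrast between a written target and local practice is softer than it first looks. That also stands, although one arm would still have a stated target and the other none.

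If the paragraph is ROTEM-only, it could be defended as part of an algorithm package compared with standard practice. That is a legitimate design, but the primary objective speaks of transfusion guided by ROTEM versus laboratory tests. A package comparison would have to be declared.

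Finally, imposing >9/>10 g/dL on control could increase transfusion there if local practice is more restrictive. This is correct, and the fix allows for it.

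None of these replies tells a provider which red-cell rule applies to a control patient.

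**Conclusion.** The point holds as an uncontrolled possible confounder of one main outcome, of unknown direction and size. It should be fixed because the remedy is cheap and the outcome is primary. The FFP outcome is not touched by this paragraph.

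A reader might go further and infer that the arms do follow different thresholds, that the RBC result is biased, or that power falls to 43%. The documents do not support this. Local practice is not described and may equal the written target, and the paragraph may already apply to both arms, in which case the effect is zero and only the wording needs repair. The tabulated figures show what any gap of that size would do; they are not evidence that a gap exists. They rest on the assumed gaps, a two-sided t-test and the plan's own SD of 5.

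**What to change.** 1. Move the red-cell paragraph to the head of Section III.4 and state that one RBC rule, with the same clinical-judgment override, applies to both arms. The investigators choose whether that rule is the written >9/>10 g/dL target or the institution's standard threshold.
2. Add that haemoglobin and blood gases are not covered by the ROTEM-arm blinding.
3. Compare by arm the haemoglobin or haematocrit and blood-gas values already collected. Unit counts and administration times are recorded too, so values before transfusion can be examined. This can show whether red-cell practice differed; it cannot fully correct the RBC effect if it did.

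Cost: one paragraph moved, a sentence or two added, and one descriptive comparison. Sample size, alpha, outcomes and data collection do not change. The downside is that RBC practice in one arm becomes slightly less like usual care. If the written target is chosen and is more liberal than local practice, control patients may receive somewhat more blood, which is why the choice of common rule stays with the investigators.
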